5.4. TRAINING CASES

Each Investigator will complete 1-5 training cases (see section 7.7.1 Training Cases Schedule of Events Table).

Training cases will be attended by a Spirox-authorized Latera trainer. Trainers may be Spirox Clinical personnel or ENT Consultant.

The following criteria will be used to determine the satisfactory completion of the training case requirement to proceed with enrollment into main study population as assessed during the Treatment Visit (Visit 3) as the:

- Successful procedure completion, and
- No device-related and/or procedure-related Adverse Events.

Upon successful completion of implant procedure based on criteria outlined above, Spirox will issue written notification of having satisfactorily completed the train case requirement. Upon receipt of the notification the individual Investigator may begin enrollment in the main study population.

Subjects enrolled as training cases will only be followed through 1 month post procedure. An investigator will not be allowed to conduct additional training cases once he/she has begun enrollment for study subjects.

5.5. PARTICIPANT WITHDRAWAL OR EARLY TERMINATION

Participants are free to withdraw from participation in the study at any time upon request. Investigators may withdraw or early terminate a subject from the study as deemed appropriate per safety measures and/or if the subject develops a medical condition that prohibits further study participation.

In the event of an early subject termination, the clinical investigational site will, at a minimum, document Adverse Events and Concomitant Medications changes, as appropriate, and all available data in the eCRFs. The clinical site will also complete the Study Exit eCRF.

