Subjects that have been enrolled and have undergone the index procedure at the time of study enrollment suspension will be followed per the study schedule through the 24-Month closeout visit. Subjects that have been consented, but not yet undergone index procedure, will be delayed until a decision about whether to restart enrollment has been made. These later subjects will be re-consented if the enrollment suspension lasts longer than thirty (30) days.

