All data collected for these visits should be entered into the EDC no later than seven (7) days after the completion of each visit. Adverse events observed through the 12 month visit will be collected and documented. Only adverse device effects will be collected beyond the 12 month visit. Spirox will be notified as necessary pursuant to the description provided in Section 8. Data collected for these visits should be entered into the EDC no later than seven (7) days after the completion of each visit.

Upon completion of the follow-up visit activities, the subject will be scheduled for the next Follow-up Evaluation Visit.

Subject participation will be complete at the 24 month follow-up time point and documented in the Study Exit eCRF.

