7.8. EARLY TERMINATION VISIT

In the event of an early subject termination, the clinical site should, at a minimum, document Adverse Events and Concomitant Medications changes. Refer to **Section 7.7** Schedule of Events.

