8. ASSESSMENT OF SAFETY

8.1. SPECIFICATION OF SAFETY PARAMETERS

All Serious Adverse Events (SAE), Adverse Device Effect (ADE) and Serious Adverse Device Effects (SADE) will be collected and documented through the end of subject participation in the study. In addition, all non-serious device and procedure-related Adverse Events (AE) and all non-serious head and neck, and/or respiratory related AEs will also be collected and documented.

The primary safety endpoint evaluation will consider nasal procedure related and Latera related adverse events through 6 months post-procedure.

The following information for each AE, ADE, SAE and SADE will be collected:

- Date of onset
- Status and/or Outcome
- Date of resolution
- Adverse Event/Effect type (See Section 8.1.1)

In the event of Implant loss or removal, the following information will be documented:

- Implant exposed intranasal at pierce point or exposed on the external skin surface
- Implant retrieved by surgeon or subject
- Whether Implant loss or removal was complete or partial
- SAE or SADE (See Section 8.1.2 and 8.1.3)
- Severity of event (See Section 8.2.1)
- Relation to Study Device and/or procedure (See Section 8.2.2)
- Action taken
- Descriptive narration of Event/Effect

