10.3. ANALYSES DATASETS

Four analysis populations will be considered: The analysis datasets described in the following section apply to the subjects enrolled in the main study (excluding training cases). The training subjects will not be included in the formal analyses for this protocol.

- Intention-to-Treat (ITT) Population: all enrolled subjects who began a nasal Implant procedure, regardless of concomitant turbinate treatment (i.e., Latera alone or in conjunction with turbinate treatment) or re-implant according to this protocol.
- Modified Intention-to-Treat (mITT) Population: all subjects enrolled who received at least one nasal Implant, regardless of concomitant turbinate treatment. Subjects that received a replacement implant will be included in this analysis dataset.
- Per-Protocol (PP) 6 Month Evaluable Population: subjects with 6 month post-Implant NOSE score assessments in clinic or by telephone, regardless of concomitant turbinate treatment. Subjects that received a replacement implant will not be included in this analysis dataset.
- Latera Stand-Alone Population: subjects who receive at least 1 Latera implant without concomitant turbinate treatment.

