11. SOURCE DOCUMENTS AND ACCESS TO SOURCE DATA/DOCUMENTS

Each participating site will maintain appropriate medical and research records for this trial, in compliance with ICH E6 and regulatory and institutional requirements for the protection of confidentiality of participants. Each site will permit authorized representatives of the study sponsor and regulatory agencies to examine (and when permitted by applicable law, to copy) clinical records for the purposes of quality assurance reviews, audits, and evaluation of the study safety, progress, and data validity.

Source data includes all information, original records of clinical findings, observations, or other activities in a clinical trial necessary for the reconstruction and evaluation of the trial. Examples of these original documents and data records include, but are not limited to, hospital records, clinical and office charts, laboratory notes, memoranda, participants' memory aids or evaluation checklists, recorded data from automated instruments, copies or transcriptions certified after verification as being accurate and complete, microfiches, photographic negatives, microfilm or magnetic media, x-rays, and participant files and records kept at the pharmacy, at the laboratories, and medico-technical departments involved in the clinical trial. Sponsor will provide Source Documents to the sites.

For each subject consented, the inclusion/exclusion source documentation must be signed by the investigator or authorized delegate from the trial staff. If a subject withdraws from the study, the reason must be noted on the Study Exit eCRF. If a Subject is withdrawn from the study because of a treatment-limiting adverse event, thorough efforts should be made to clearly document the outcome.

All forms shall be filled out using indelible ink and must be legible. Errors shall be crossed out but not obliterated and correction inserted and the change initialed and dated by the investigator or authorized delegate. The investigator shall ensure accuracy, completeness, legibility and timeliness of the data reported to the sponsor in the eCRF and in all required reports.

Each investigator/institution agrees that they will permit trial-related monitoring, audits, IRB review and regulatory inspections by providing direct access to source data and/or documents.

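### Section 5.5 does not separate ending study procedures from ending data collection, so 6-month NOSE scores and later device events of implanted subjects can be lost selectively

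*Combined protocol and SAP*

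**What the plan says.** Section 5.5 gives the investigator two grounds for ending participation: "Investigators may withdraw or early terminate a subject from the study as deemed appropriate per safety measures", or a medical condition that rules out further participation. Both end participation in the study as a whole. Neither distinguishes stopping study procedures from stopping data collection.

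At early termination the site must, under 5.5, "at a minimum, document Adverse Events and Concomitant Medications changes, as appropriate, and all available data in the eCRFs", and complete the Study Exit eCRF. Section 7.8 repeats the minimum: "the clinical site should, at a minimum, document Adverse Events and Concomitant Medications changes". Neither section asks for a NOSE score at exit or for any contact afterwards.

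Section 8.1 states that serious events and device effects "will be collected and documented through the end of subject participation in the study". After month 12 the enquiry narrows: "Only adverse device effects will be collected beyond the 12 month visit" (section 7.1.5). Section 8.3 follows events to resolution or to the 24-month visit, but gives no means of finding new events after a subject has left.

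Section 5.6 takes a different line for a different situation. Subjects who have "undergone the index procedure at the time of study enrollment suspension will be followed per the study schedule through the 24-Month closeout visit".

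Section 11 has a sentence beginning "If a Subject is withdrawn from the study because of a treatment-limiting adverse event". It asks for thorough efforts to document the outcome, and the same section requires the reason for withdrawal on the exit form.

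**The concern.** The index treatment is given once, at Visit 3. The only further study treatment is the optional re-implantation of section 7.1.6, three to five months after the index procedure. The rest of follow-up is questionnaires, nasal examinations, imaging and adverse-event enquiry. Ending an implanted subject's participation does not undo the exposure, but under the current wording it does end the NOSE scores and the search for new device events.

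One of the two grounds is safety, so the loss can be related to outcome. There is no control arm in which a similar loss could be seen. The primary analysis (section 10.4.2) uses the mITT set but states no rule for a missing 6-month score. The sensitivity analyses for missing data are only ones that may be included, with details left to a later SAP. Section 10.4.5 compares baseline features of subjects with and without 6-month scores, which cannot show whether outcomes differ. No imputation recovers an unobserved device event, and device-related events are the primary safety endpoint to month 6 and a secondary endpoint to month 24.

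**Working it through.** **Inputs from the plan (section 10.5).** Null rate 0.50; exact two-sided 5% test; assumed true rate 0.66; 150 subjects with 6-month data; up to 170 enrolled for about 10% dropout.

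**The plan's own figure.** The upper-tail critical value c is the smallest count with P(X ≥ c | n, 0.50) ≤ 0.025.
- At n = 150, c = 88, upper-tail error is 0.0204 and power at 0.66 is 97.5%. This agrees with the stated power above 90%.
- Dropout: 150/0.9 = 167, against 170 enrolled.
- At n = 170 with complete follow-up, c = 99 and upper-tail error is 0.019.

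**Assumptions the plan does not supply.** All 170 are implanted. Subjects without a 6-month score drop out of the denominator (observed-case scoring). The number w withdrawn by investigators before month 6 is 5, 10 or 17, where 17 is 10% of 170. Their response rate r is either 0 or half the true rate p.

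**Formula.** Observed rate q = (170p − w·r)/(170 − w). Chance of an upward rejection = P(X ≥ c | n = 170 − w, q), with c = 96, 93 and 90 at n = 165, 160 and 153. At a true 0.50 with no selective loss, that chance is 1.8% to 2.4% at these n.

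**True response 66%** (170 × 0.66 = 112.2):

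| w | r = 0 | r = 0.33 |
|---|---|---|
| 5 | 112.2/165 = 68.0% | 110.55/165 = 67.0% |
| 10 | 112.2/160 = 70.1% | 108.9/160 = 68.1% |
| 17 | 112.2/153 = 73.3% | 106.59/153 = 69.7% |

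**True response 50%** (170 × 0.50 = 85), false-positive risk in the favourable direction:

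| w | r = 0 | r = 0.25 |
|---|---|---|
| 5 | q = 0.515, 5.1% | q = 0.508, 3.3% |
| 10 | q = 0.531, 11.7% | q = 0.516, 5.7% |
| 17 | q = 0.556, 23.3% | q = 0.528, 7.8% |

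**Robustness of the test.** These checks allow 20 missing subjects (170 − 150) and count them all as non-responders.
- 88/150 (p = 0.041) becomes 88/170 = 51.8% (p = 0.70).
- 99/150 (66%) becomes 99/170 = 58.2% (p = 0.038) and stays significant.

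**What the documents show about actual loss.** They give no count of investigator withdrawals and no split of exit reasons. In the prior German study (section 2.2), 4 of 30 subjects had device-related events, but the NOSE table shows all 30 with a 6-month score. The three exits described there followed other nasal surgery and came after the 12- or 18-month visit.

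**The case against.** The other side has five fair points.

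- **Section 5.5 is wider than the implanted subject doing badly.** Subjects count as enrolled at the end of screening (section 7.1.1), so some withdrawals precede the implant and fall outside mITT. A medical condition that ends participation may have nothing to do with the nose or the device. A reader might infer that data go missing mainly for subjects doing badly, but the text does not establish this. Participant request and loss to follow-up also cause missing scores. What stands is that loss can be selective.
- **Withdrawal is not empty of purpose.** Follow-up includes repeated endoscopy, re-implantation is possible, and section 7.6 bars several other nasal treatments. A reader might infer that ending participation protects nobody. The documents do not support that.
- **The prior study's 4 of 30 is not a withdrawal rate.** All 30 subjects had a 6-month score.
- **Observed-case scoring is assumed.** Section 10.5 says all mITT subjects enter the comparison, and section 10.4.2 classes as non-responders those who meet neither criterion. That can be read to include subjects with no score. The plan is ambiguous here. Counting missing as non-response would remove the upward bias in the primary proportion, but the plan does not commit to it and it would not recover device events. The repeated-measures VAS model uses earlier visits and is valid if loss depends only on observed scores.
- **Known events are covered.** Sections 8.3 and 11 follow them up, and the reason for withdrawal is recorded. Neither section provides for new events after exit or for a 6-month NOSE score.

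**Conclusion.** The point holds as a gap in data collection. Followed as written, section 5.5 with 7.8 and 8.1 lets an implanted subject leave on safety or medical grounds with no 6-month NOSE score and no search for later device events. Section 5.6 already accepts the opposite principle when enrollment is suspended.

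The size is conditional on assumed withdrawal counts and observed-case scoring. Inflation is 1.0 to 7.3 percentage points at a true 66%, and the upper-tail false-positive risk is 3.3% to 23.3% at a true 50%, against about 2%. The top of each range is close to a worst case: investigator withdrawals alone would use the whole 10% dropout allowance, and every withdrawn subject would be a non-responder.

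A reader might infer that the primary conclusion is unsafe. At the assumed 66% it is not, because rejection of 0.50 is expected to survive. The harm is mainly to the estimated response rate, to the test if the true rate is near 50% to 60%, and to the count of late device events.

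**What to change.** State in sections 5.5 and 7.8 that, when an investigator ends study procedures for an implanted non-training subject, the scheduled NOSE scores and adverse-event or device-effect enquiries continue to month 24 unless the subject withdraws consent. Where a visit is not possible, collect them by telephone. The plan already accepts remote collection: the per-protocol set in section 10.3 admits "subjects with 6 month post-Implant NOSE score assessments in clinic or by telephone", and section 5.3 allows telephone or mailed follow-up at months 18 and 24. Record on the Study Exit eCRF whether the subject or the investigator ended participation, besides the reason.

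This concerns data collection only. Which procedures to stop for safety remains the investigator's decision. The rule should not extend automatically to site closure or study termination: the closure grounds in section 5.6 include false data and non-compliance, where continued collection at that site may be undesirable.

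The cost is a few sentences of protocol wording, one exit-form field and a few extra telephone contacts. The reported response rate may be lower as a result.

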5.6. PREMATURE TERMINATION OR SUSPENSION OF STUDY

The study enrollment may be temporarily suspended or prematurely terminated if there is sufficient reasonable cause. Written notification, documenting the reason for enrollment suspension or study termination, will be provided by the Sponsor to the investigator and regulatory authorities. If the study is prematurely terminated or enrollment suspended, the site PI will promptly inform the IRB(s) and will provide the reason(s) for the termination or suspension.

Both the sponsor and the investigator reserve the right to terminate the study at any time. In terminating the study, the sponsor and the investigator will assure that adequate consideration is given to the protection of the subjects' interests.

If the sponsor, investigator, study monitor, or appropriate regulatory officials discover any conditions arising during the study that indicate that the study enrollment should be suspended or that the study site should be terminated, this action may be taken after appropriate consultation among the sponsor, investigator, and study monitor. Conditions that may warrant enrollment suspension or termination of the study site or of the study itself, may include, but are not limited to, the following:

- The discovery of an unexpected, serious, or unacceptable risk to the subjects enrolled in the study;
- A decision on the part of the sponsor to discontinue the study;
- A decision on the part of the sponsor to suspend enrollment or discontinue evaluation of the device;
- A request from a regulatory authority;
- Failure of the investigator to enroll subjects into the study at an acceptable rate;
- Failure of the investigator to comply with pertinent regulations of appropriate regulatory authorities;
- Submission of knowingly false information from the research facility to the sponsor, study monitor, or appropriate regulatory authority;
- Insufficient adherence to protocol requirements.
- Determination that it is unlikely that the study null hypothesis can be rejected

In the event of enrollment suspension, the study may resume once concerns about safety, protocol compliance, or data quality are addressed to the satisfaction of the sponsor, IRB and/or FDA.

Subjects that have been enrolled and have undergone the index procedure at the time of study enrollment suspension will be followed per the study schedule through the 24-Month closeout visit. Subjects that have been consented, but not yet undergone index procedure, will be delayed until a decision about whether to restart enrollment has been made. These later subjects will be re-consented if the enrollment suspension lasts longer than thirty (30) days.

6. STUDY DEVICE

6.1. STUDY DEVICE ACQUISITION

The Latera™ System (Absorbable Nasal Implant and Delivery Device) is a commercially available device that has received FDA clearance (K161191). The device will be used under this study protocol in accordance with the cleared indications for use and instructions for use and provided to the investigators at no charge by Spirox, Inc.

6.2. STUDY DEVICE DESCRIPTION AND INDICATIONS FOR USE

The Latera Absorbable Nasal Implant is indicated for supporting nasal upper and lower lateral cartilage. The absorbable nasal Implant is comprised of a 70:30 blend of poly(L-lactide) and poly(D-lactide). The Implant is predominantly cylindrical in shape with a diameter of 1 mm and an overall length of 24 mm with a forked distal end for anchoring and features on the proximal end for increased flexibility. The copolymer is absorbed by the body over a period of approximately 18 months²². The Implant is provided in a plastic tray with a sliding lid. The Implant and plastic tray are depicted in Figure 1 below.

Figure 1: Latera Absorbable Nasal Implant and Packaging

The Delivery Device is a single use device composed of a handle body, deployment plunger and pushrod, and a 16-gauge delivery cannula with a depth marker and protective cover. The handle includes an Implant loading port which enables the loading of the Implant. The handle uses an internal transition between the loading position and the cannula to collapse the Implant forks within the cannula inner lumen and prepare the Implant for deployment. The Implant Positioning Guide is packaged with the Delivery Device to aid the physician in preparing for the procedure and identifying the target Implant location. The Delivery Device and the Implant Positioning Guide are shown in Figure 2 below.

[figure not shown]

Figure 2: Delivery Device and Implant Positioning Guide

6.3. STUDY DEVICE STORAGE AND STABILITY

Follow Instructions for Use. The Implants are shipped in insulated containers containing frozen ice packs to protect the product from reaching high temperature. The Implants must be stored in a cool, dry location at or below 30°C. The Delivery Devices are shipped in cardboard boxes and are not subject to special shipping, storage or temperature requirements.

6.4. STUDY DEVICE PREPARATION AND IMPLANTATION

Instructions regarding the device preparation are provided in the Instructions for Use (IFU) (see Appendix III Latera IFU).

6.5. STUDY DEVICE ACCOUNTABILITY PROCEDURES

Accurate records of all study devices received and used to treat subjects, returned to the Sponsor, or designee, or destroyed at the study site, shall be maintained by the site. No Implants or Accessory Devices (Latera System) are to be destroyed or returned without authorization from the Sponsor. The lot number of each unit used will be tracked on the subject's eCRF and on each site's device accountability log.

Latera study devices will be provided by Spirox for use under this study protocol only. The investigators will not provide these devices to a third party, nor will he/she allow use of these devices outside of this study protocol.

7. STUDY PROCEDURES AND SCHEDULE

The procedures and schedule detailed in this section are applicable as noted, to both training case and non-training case subjects. Training cases are followed through 1 month, whereas non-training cases are followed up through 24 months. Refer to section 7.2 for schedule of events.

7.1. STUDY VISIT SPECIFIC PROCEDURES

7.1.1. Subject Screening and Enrollment Visit (Visit 1) (All Subjects)

All subjects seeking treatment for nasal obstruction will be screened for eligibility according to the inclusion/exclusion criteria. A member of the research team will review the subject's medical history for eligibility and inclusion into the study.

The subject will be asked to fill out a NOSE score questionnaire and a NOSE score will be calculated. If all inclusion criteria (including NOSE score ≥ 55) are met and no exclusion criteria are present, the Investigator will inform the subject about the purpose of the study. The background of the proposed study along with the potential benefits and risks will be explained to the subject and questions will be answered. Potential subjects will be counseled as to the nature of their condition. All subjects will have ample time to ask questions.

Subjects indicating that they would like to proceed with study participation, and who are willing to comply with the requirements of the study protocol, will be asked to sign an Informed Consent Form (ICF) that has been approved by the governing IRB. Failure to provide written informed consent renders the subject ineligible for the study.

Female subjects of childbearing potential will undergo a pregnancy test to verify eligibility. Women of childbearing potential are defined as any female who has experienced menarche and who is NOT permanently sterile or postmenopausal. Postmenopausal is defined as twelve (12) consecutive months with no menses without an alternative medical cause.

Subjects that have signed the ICF and met eligibility criteria will be scheduled for Visit 2. Subjects will be considered enrolled upon signing the ICF, meeting study eligibility criteria, at the completion of the screening visit.

Study data including any adverse events that occurred after the ICF was signed, should be entered into the EDC within 24 hours of completion of the visit.

Subjects that have provided written informed consent and met the eligibility criteria may also be invited to participate in "Latera™ Patient Experience and Testimonials" (see Section 7.2.16 below).

